Study Rationale	The purpose of the present study is to investigate the barriers and facilitators to implementing a moderated online social media platform with therapeutic content, Horyzons, as a part of routine care received at first-episode psychosis (FEP) clinics across North Carolina.
Study Objective(s)	
Examine the implementation and integration Horyzons at NC FEP clinics as part of routine clinical care through the following objectives:
 
 1. Identifying the unique barriers and facilitators in implementing Horyzons at each FEP clinic as part of standard care and distinct implementation strategies 2. Evaluate client engagement with Horyzons and attrition as part of clinical care across 12 months 3. Assess change in clients' psychological measures across 12 months and use of emergency and social services across 12 months prior and during engagement with Horyzons platform
Test Article(s) (If Applicable)	Horyzons is a private digital platform that includes curated therapeutic content surrounding issues such as generalized anxiety, social anxiety, social functioning, depression, and distress tolerance. The site also includes a social media function, in which participants and peer support specialists (PSS) can post text, images, and videos. The site is moderated by graduate students and trained fs.
Study Design	This is an open trial enrolling both clients from NC FEP clinics and clinicians and PSSs. FEP clients will participate in the use of Horyzons, a novel digital intervention, which has previously demonstrated benefits to this population and complete psychological measures. FEP clinicians and PSSs will take part in qualitative interviews and surveys to identify unique barriers and enablers in integrating Horyzons as a clinical service within FEP clinics.
Client Participants	
Inclusion Criteria
 
Key Criteria for Inclusion and Exclusion:
 
 1. Clients must be between the ages of 16 and 35 2. Clients must have a diagnosis of schizophrenia, schizoaffective disorder, schizopreniform disorder, or Unspecified Schizophrenia Spectrum or Other Psychotic disorder 3. Clients must be receiving services at one of the five FEP clinics in North Carolina (OASIS, Encompass, Eagle, SHORE, or AEGIS) or one of their stepdown outpatient clinics (STEP and TIDES) 4. Clients must not have had thoughts of harming themselves in the month before enrollment

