Young people receiving services from CSC programs typically attain significant positive outcomes including decreased rates of hospitalization and improved social and occupational functioning within an average of two years of treatment (2). However, treatment benefits are usually not maintained over time (3-4) in particular when clients are less engaged in treatment or have recently experienced discharge from the program. For instance, the benefits of early intervention seen at the end of 2 years may not persist at 5 years (5). There is a need, therefore, to explore ways to provide ongoing support for individuals experiencing first episode psychosis. This support should address especially what some have called "social network crisis" experienced by the FEP population. This refers to the limited social networks and community support that individuals with psychosis generally have. Innovative approaches through internet-based interventions may shed valuable light on the issue of maintaining treatment effects derived from FEP services and offer additional social support to those enrolled in such services.

Additionally, the proposed research is aligned with the NIMH strategic objective of striving for prevention and cures through the study of mechanisms of therapeutic action. Specifically, it aligns with the goals of developing new treatments based on discoveries in the behavioral sciences and testing interventions for effectiveness in community practice settings. This project in essence builds and extends the findings of research on the effectiveness of CSC and looks to determine whether these benefits can be extended beyond CSC in a web-based platform delivered to individuals in the community.

We suggest that internet-based interventions have the potential to provide cost-effective, non-stigmatizing, constantly available support to FEP people. These interventions, especially those aimed to strengthen social networks, can be used to counteract social isolation and disadvantage; increase functional outcomes and engagements (6); reduce symptomatology; and improve uptake and acquisition of therapeutic strategies. These also provide an entirely new approach in which participants can safely self-disclosure, take positive interpersonal risks, gain perspective, broaden and rehearse coping skills, obtain encouragement and validation, and learn how to solve problems (7).

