2 RESEARCH DESIGN AND METHODS

2.1 OVERVIEW

Client participants will be given access to Horyzons (which is considered a “non-significant risk” medical device and is described below) from their date of enrollment through an intervention period of approximately 12 months. Horyzons will be monitored daily (two hours per weekday & one hour per weekend day) by trained peer support specialists, master's level clinicians, licensed clinical psychologists, and/or graduate students in the Department of Psychology and Neuroscience or Social Work at UNC. To facilitate and monitor engagement, a protocol is in place that directs moderators to contact participants via text message and/or email if he/she/they have not logged onto the platform for two weeks, and via telephone if a participant remains inactive for an additional two weeks. Licensed Clinical Psychologists, [name] and/or [name] will lead weekly supervision calls to ensure appropriate care and support of clients involved in this project, to discuss case conceptualization and suggestions for engaging clients in the platform, as well as to monitor any potential safety concerns.

[Overview of Horyzons](#). Horyzons is an online social media platform that integrates: i) peer-to-peer on-line social networking; ii) individually tailored interactive psychosocial interventions; and (iii) expert moderation.

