2.2.1 INCLUSION CRITERIA

1. Clients must be between the ages of 16 and 35
2. Clients must have a primary diagnosis of schizophrenia, schizoaffective disorder, schizopreniform disorder, or Unspecified Schizophrenia Spectrum or Other Psychotic disorder
3. Clients must be receiving services at one of the five FEP clinics in North Carolina (OASIS, Encompass, Eagle, SHORE, AEGIS) or FEP clinics stepdown care clinics (STEP and TIDES)
4. Clients must not have had thoughts of harming themselves in the month before enrollment
5. Clients must not have been hospitalized for psychiatric reasons in the three months before enrollment
6. Clients must have been actively engaging in psychiatric medication management in the prior month
7. Clients must have access to the internet through a phone, tablet, or computer

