3 ASSESSMENT OF DATA

At this stage of treatment development, specific outcomes include:

1. Identifying barriers and facilitators of implementing Horyzons at NC FEP clinics through the following:
 - Conducting qualitative interviews following the CFIR framework to identify individual-, inner-, and outer-setting climate and implementation of evidence-based practices within each clinic
 - Administration of quantitative measures pre-, mid-, and post-intervention to further assess barriers and facilitators experienced by providers and PSSs in the integration and implementation of Horyzons
2. Evaluation of engagement of the platform and attrition of client participants across 12 months to assess acceptability of Horyzons as a routine clinical intervention within NC FEP clinics.
3. Evaluation of psychological outcomes (loneliness and social support) in addition to use of services (e.g., emergency department, hospitalization, outpatient services) to assess potential benefits (e.g., stability in symptoms) as a result of engagement with Horyzons.

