4.3 Client Procedures

Upon completion of the 12-month intervention period, research staff will collect and amalgamate the passive engagement information of each participant on the platform to assess acceptability and feasibility of Horyzons as part of clinical care. Additionally, client participants' medical records will be examined for service use (e.g., emergency room visits, hospitalizations, outpatient care, etc.) as a result of their mental health.

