5.3 TERTIARY OUTCOME MEASURES

1. Change in Engagement with the Horyzons Platform and Attrition over time [Time Frame: up to 12 months]

Changes in engagement with Horyzons will be passively collected for client participants via the platform. Data evaluated will include number of logins, number of journeys, tracks, and activities completed, and number engagements on the community page.

2. Change in use of emergency and social services [Time Frame: Pre- and Post-intervention, up to 12 months]

Collection of use of emergency and social services pre-initiation and post-initiation of Horyzons will be assessed to determine change in use of such services.

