8 RECRUITMENT STRATEGY

Client study subjects will be drawn from the five first episode psychosis clinics in North Carolina (OASIS, Encompass, SHORE, Eagle, and AEGIS). The OASIS clinic was co-developed by [name] for the treatment of people with first episode schizophrenia. Currently, each clinic has a census of approximately 100-150 people and admits approximately 3-5 people per month. Approximately 40 client participants will be recruited from the five clinics, or around 6-8 client participants per clinic. Additionally, all providers have been self-identified as clinicians or PSS providing services to clients at one of the five participating clinics; therefore, we expect approximately 20 providers and/or PSS to participate in this project. As such, we expect that we will be able to recruit the number of participants we would like to involve in this project.

Once a client is referred to the study (or self refers), a study clinician or research assistant will speak with the individual (and any other individuals that she/he indicates, such as a family member) to describe the study protocol, expectations of study participation and potential study risks and benefits. If a client contacts a member of the research project to indicate interest in the study, a member of the research team will explain the study over the phone and use the screening questions to assess potential eligibility. Providers and PSSs will be contacted by phone and/or email in order to obtain consent and schedule focus groups.

Recruitment will be completed by the study coordinator, research assistant, and/or clinical providers involved in this project. The latter includes peer support specialists and providers at the local FEP clinics.

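### Psychiatric admissions are compared over 9 at-risk months before Horyzons and 12 after, because eligibility forces zero admissions in the last 3 pre-months

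*Combined protocol and SAP*

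**What the plan says.** - **Comparison.** Study Objective 3 in the synopsis is to assess "use of emergency and social services across 12 months prior and during engagement with Horyzons platform". Section 5.3 item 2 states that use "pre-initiation and post-initiation of Horyzons will be assessed to determine change in use of such services". It gives no model, denominator or adjustment.
- **Content.** Section 5.3 item 2 names emergency and social services. Hospitalization enters through Section 3 item 3 and through Section 4.3, where "medical records will be examined for service use (e.g., emergency room visits, hospitalizations, outpatient care, etc".
- **Eligibility.** Inclusion criterion 5 (Section 2.2.1, repeated in the synopsis): "Clients must not have been hospitalized for psychiatric reasons in the three months before enrollment".
- **Start of the post-period.** Section 2.1 gives access "from their date of enrollment through an intervention period of approximately 12 months". The admission-free window is therefore the last quarter of the look-back.
- **Intended use.** Section 3 item 3 will use these data "to assess potential benefits (e.g., stability in symptoms) as a result of engagement with Horyzons".

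**The concern.** A before/after comparison of counts is fair only if the event could be recorded for the same length of time in each period. Here every enrolled client has, by design, no psychiatric admission in the three months before enrollment, and no such condition applies after it. The pre-period count is therefore low for a reason unrelated to the clients' course or to Horyzons.

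Taken alone, this makes admissions appear to rise once clients join the platform, and it can hide a real fall. Section 5.4 says that the study will inform future implementation of Horyzons in North Carolina, so a misleading admissions figure could carry weight even though the outcome is tertiary.

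**Working it through.** The documents give no admission rate and no expected ratio, so there is no figure of the plan's own to reproduce. The check is person-time arithmetic.

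**Inputs from the documents.** Look-back of 12 months and follow-up of 12 months (synopsis, Objective 3); admission-free window of 3 months (Section 2.2.1); clients: up to 50 (Section 2.2) or approximately 40 (Section 8).

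**Assumption, not in the documents.** 0.2 to 0.4 psychiatric admissions per client-year.

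**Step 1: months at risk.** Before: 12 - 3 = 9. After: 12.

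**Step 2: ratio under no effect.** With a constant rate the rate cancels, so the expected post/pre ratio is 12/9 = 1.33. It does not depend on the assumed rate. Nor does it depend on clients having equal rates: simulations that select on zero admissions in the last 3 months, with equal or gamma-distributed client rates, give raw ratios of 1.33 to 1.34 and ratios per month at risk of 1.00.

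**Step 3: masking.** A true rate ratio of 0.75 shows as 0.75 × 12/9 = 1.00.

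**Step 4: what this means at the planned size.** Expected counts are N × rate × 9/12 before and N × rate after. The probabilities are exact Poisson calculations under no effect. A false rise means post above pre at the 5% level in an exact two-sided conditional test.

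| Clients | Rate per year (assumed) | Expected before vs after | P(post > pre) | P(post > pre) if 12 vs 12 months at risk | False rise, raw counts | False rise, 9:12 offset |
|---|---|---|---|---|---|---|
| 50 | 0.4 | 15 vs 20 | 0.777 | 0.468 | 9.8% | 2.0% |
| 50 | 0.2 | 7.5 vs 10 | 0.684 | 0.455 | 5.5% | 1.8% |
| 40 | 0.4 | 12 vs 16 | 0.746 | 0.465 | 7.8% | 1.9% |
| 40 | 0.2 | 6 vs 8 | 0.655 | 0.450 | 4.5% | 1.6% |

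The plan specifies no test, so the last two columns are illustrative. The two-sided convention matters slightly: with doubled tails the offset column runs from 1.3% to 1.6%.

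**Step 5: a rate that was already falling.** Let the admission rate in months -12 to -4 be k times the post-period rate for reasons unrelated to Horyzons. The raw ratio is then 12/(9k) and the ratio per month at risk is 1/k.

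| k | Raw ratio | Per month at risk |
|---|---|---|
| 1 | 1.33 | 1.00 |
| 1.33 | 1.00 | 0.75 |
| 2 | 0.67 | 0.50 |

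**Step 6: why k may exceed 1.** No minimum time in clinic is required. Section 8 says that "each clinic has a census of approximately 100-150 people and admits approximately 3-5 people per month". The share of a census that entered within the last 12 months is therefore between 12 × 3/150 = 24% and 12 × 5/100 = 60%, if no recent entrant has left and enrollees resemble the census. For those clients the look-back reaches into time before specialty care, which Section 1 associates with "decreased rates of hospitalization and improved social and occupational functioning within an average of two years of treatment". The documents do not allow k itself to be estimated.

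**The case against.** The case on the other side has five parts.

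1. *The admissions comparison is assembled from several sections.* Objective 3 and Section 5.3 item 2, which state the before/after contrast, name emergency and social services. Hospitalization appears as an example in Sections 3 and 4.3. This is true, and it is a reason to state the components explicitly. Section 3 item 3 nevertheless lists hospitalization as part of this same outcome, and emergency visits ending in a psychiatric admission are affected on any reading.
2. *The 1.33 needs a constant rate.* It does. If k = 1.33 the raw ratio is exactly 1.00. But two opposing biases do not make the raw comparison fair. One of them is known exactly and can be removed.
3. *Correcting only the structural zero may flatter Horyzons.* This stands. Where rates were already falling, the corrected null ratio is 1/k, below 1. The report must say so. Restricting to clients with longer tenure lessens this but does not remove continuing recovery.
4. *The 24-60% for recent entry may be too high.* It comes from figures for the five first-episode clinics. Clients may also come from the step-down clinics, where tenure is probably longer, and Section 4.1.1 looks for clinically stable clients. This also stands: the range is an indication, not an estimate for the enrolled sample.
5. *This is one component of a tertiary outcome in an unpowered, single-arm study.* That limits the severity. It does not make a ratio with a built-in factor of 12/9 suitable for judging benefit.

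**Conclusion.** The concern holds and should be fixed. The 3-month structural zero, the 9 against 12 months at risk and the absence of any adjustment all follow from the documents. Under a constant rate the artefact multiplies the post/pre ratio for psychiatric admissions by 1.33, enough to cancel a true 25% reduction. At 40 to 50 clients and the assumed 0.2 to 0.4 admissions per client-year, post exceeds pre in about 66% to 78% of trials with no effect, against 45% to 47% with equal time at risk.

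The net direction of bias in the raw comparison is unknown, because recent clinic entry and natural recovery may act the other way. The finding is confined to psychiatric admissions and emergency visits ending in one. Criterion 5 does not force other emergency visits, outpatient care or social services to zero, and the primary outcomes and psychological measures are untouched.

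**What to change.** In Section 5.3 item 2:

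1. Report hospitalization, emergency use, and outpatient and social-service use separately.
2. For psychiatric admissions, and emergency visits ending in one, compare rates per month at risk within client: months -12 to -4 against months 1 to 12 after initiation, using actual months of follow-up. A conditional Poisson model with client as stratum and log months at risk as offset would do this. Report the rate ratio with its 95% confidence interval.
3. Keep the full 12-month look-back for the other services.
4. Record each client's clinic-entry date and add a sensitivity analysis restricted to clients with at least 12 months in clinic before enrollment, so that the same clients contribute to both periods. Do not cut individual pre-periods at clinic entry.
5. State that the comparison is uncontrolled and descriptive, and that natural recovery or regression to the mean could make the corrected ratio look favourable.

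In Section 3 item 3, replace the attribution of benefit to engagement with a neutral phrase such as *during access to Horyzons*.

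**Cost.** Wording in two sections and one date from records already being examined. No admission is lost, since the dropped window contains none by design, but a 3-month gap is left before initiation. The sensitivity sample is small: 0.40 × 40 = 16 to 0.76 × 50 = 38 clients, on the census assumption above. Precision stays poor: at 15 against 20 admissions the confidence factor is exp(1.96 × √(1/15 + 1/20)) = 1.95, so the interval around a rate ratio of 1.0 is about 0.51 to 1.95.

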5.4 POWER ANALYSIS

We did not conduct a priori power calculations to determine a sample size with 80% power because this is an exploratory study and will inform future implementation of Horyzons in North Carolina as part of clinical services.

5.5 DATA MANAGEMENT

We will use the REDCap system to facilitate data entry and management, including informed consent. We will leverage features in REDCap such as real-time data validation, built-in integrity checks, and other mechanisms for ensuring data quality (i.e., double data entry). Our team will use the NVivo program for qualitative analysis. DocuSign's HIPAA compliant informed consent system will be used to obtain informed consent and electronic signature from participants.

6 RISKS AND BENEFITS

Risks for all participants. Identifying research subjects by a study number on all research documents minimizes risk of breach of confidentiality. Study documents that must contain personal information, such as the document that links study ID number to personal identifying information (necessary due to the longitudinal nature of this study) are kept in locked filing cabinets in locked rooms. Research data is kept on password-protected drives, and our computer systems are HIPAA compliant. All study staff participate in annual human subjects training that includes education about responsibilities to minimize risk that confidentiality may be breached.

Risks for clients only. Risk of anxiety, paranoia, and/or shame/embarrassment due to experiences using this online platform is minimized by completion of a Horyzons induction procedure. This will also be mitigated through the use of consistent moderating of the site as well as moderators' use of a nonjudgmental clinical attitude. The informed consent process will be completed in private spaces within the clinic/research setting or via video conferencing will be done in secure locations and on secure servers. The participant will be instructed via email or phone call before the interview to find a private location to complete the induction to the platform. Additionally, consent forms will be sent to the participant using a secure UNC email account. Documents will not contain confidential information.

Risks for providers only. The informed consent process will be completed in private spaces within the clinic/research setting or via video conferencing will be done in secure locations and on secure servers. Providers and/or PSS will be instructed via email or phone call before the interview to identify an appropriate location (i.e., private space) if held virtually rather than in person. All documents such as consent documents and surveys will be sent to providers and/or PSS using a secure UNC email account. Documents will not contain confidential information.

6.1 Monitoring Risks

To address subject anxiety or embarrassment due to revealing person information, we have trained research staff who are experienced in working with individuals with schizophrenia spectrum disorders. They have been trained to put subjects at ease, let them take their time, and to conduct interviews in private rooms.

To address the issue of accidental disclosure of personal information to others outside of the research staff, we will identify research subjects by study number on all research documents to minimize the risk of breach of confidentiality. Study documents that must contain personal information, including the informed consent document, and the document that links study ID number to personal identifying information are kept in locked filing cabinets in locked rooms. Research data will be kept on password-protected drives, and our computer systems are HIPAA compliant. All study staff participate in annual human subject training that includes education about responsibilities to minimize risk that confidentiality may be breached.

Online safety. Privacy and online safety will be managed in accordance with the 'Online social networking' guidelines published by 'Cybersmart', a national cybersafety and cybersecurity education program managed by the Australian Communications and Media Authority (ACMA). Cybersmart is designed to meet the needs of its target audiences' young people, parents, teachers and library staff. Information about Cybersmart can be found at <http://www.cybersmart.gov.au/>, while the guidelines are available at <http://www.acma.gov.au/>.

Safe and informed orientation to the system will be a priority for the research team. Peer support specialists, clinicians, research coordinator, and/or a graduate student in the Department of Psychology and Neuroscience at UNC-CH will meet with each participant to provide them with login information, help set up their account and orient them to the Horyzons system, including details of the terms of use. All users of Horyzons will be asked to nominate an emergency contact person, such as a close family member. The terms of use explain to users that information passed onto moderators or communicated within the system that may indicate concerns regarding their wellbeing may be communicated with their treating team or private practitioner. Hard copies of 'Horyzons Terms of Use' will be provided to users which will be made available online and in printed form. Participants will be required to sign the hard copy as well as accepting the terms of use on entry into the system. The system also includes a "report function" which enables users at any time to indicate to the moderator a concern about any material posted by a user, including concern about potential abuse or concerns about the wellbeing of another participant. The moderator will assess the basis of the report and respond accordingly, which can include the removal of the material or deactivation of an account.

In addition, users will be able to "switch off" their profile and hide all of their existing comments on the system should they become concerned about their privacy during their course of participation. The limits of the moderator's ability to respond (e.g., in a timely manner to emergencies) will also be fully explained. In order to protect the privacy of users who discontinue using the system, any accounts that have not been activated for one month may be deactivated following a follow-up telephone call from the moderator. Specifically, our disengagement protocol is such that a participant will receive an email/call/text message if they have not logged onto the platform for two weeks. If another two weeks pass, we will call this person to check in about any potential issues or concerns. If participants do not comply with the guidelines for safe use of Horyzons (e.g., discriminatory comments towards other users) they will be excluded from the system.

Clinical safety. Clinical risk will be managed through manual and automated procedures. Information related to clinical risk will be screened twice daily by moderators (in the morning and late afternoon/evening). This information can include: 1) post made by participants, which disclose evidence of psychotic, depressive or suicidal symptoms; 2) participants reports or complaints of posts made by other users; 3) risk or self-harm related words automatically detected and blocked by the system; and 4) presence of Early Warning Signs of relapse detected by the regular monitoring of psychotic symptoms implemented within Horyzons.

Any detected increased risk will activate the Horyzons crisis protocol which includes a number of potential actions. Initially, the moderator will conduct a risk assessment based upon available information, inform the research team, and emergency contact nominated by the participant, and liaise with suitable emergency services where necessary. In addition, the system incorporates visible emergency guidelines and contact information (i.e., on every webpage).

An automated keyword system has also been built in Horyzons which will be activated each time a participant posts a contribution containing the words or phrases: suicide, die, kill myself/you/him/her/them, hang myself/you/him/her/them, harm myself/you/him/her/them, snort, shoot up, burn myself/you/him/her/them, cut myself, drown myself/you/him/her/them, stab myself/you/him/her/them, slit, slice, electrocute, shoot myself/you/him/her/them, top myself, jump in front of, jump off, end it all, sleep and never wake up, death, die, asphyxiate, or gas. When these words are detected, the contribution will be blocked and the participant will be sent an automated message explaining that the content has been blocked and if they are facing distress then they should contact the emergency contact number as soon possible or if they are not facing distress, they may like to consider rephrasing their post. An automated message will also be sent to the Horyzons moderator containing the attempted post.

In addition, a message will be available on each page providing a cell phone number carried by a member of the research team for any emergencies that are related specifically to the use of the Horyzons system (e.g., highly inappropriate use of the system). Further, each page includes an "In case of emergency" link that provides information about ways to contact emergency services (911), the UNC crisis line [contact]), and crisis services (988; <http://crisisolutionsnc.org/>).

